3.3 Other secondary efficacy variables

Other secondary efficacy variables are:

- Proportion of patients achieving HbA1c of <7% (and <7.5%) without confirmed hypoglycaemia at week 52
- Proportion of patients achieving HbA1c of <7% (and <7.5%) at Week 52
- Proportion of patients achieving individually agreed HbA1c targets at Week 52
- Proportion of patients achieving an HbA1c decrease of ≥1% with no weight gain at week 52
- Time spent below HbA1C target (<7%) (and <7.5%) during the 52-week double-blind treatment period
- Change in body mass index (BMI) from baseline to week 52
- Proportion of patients achieving weight reduction of $\geq 5\%$ from baseline to week 52
- Proportion of patients with weight gain $\geq 5\%$ from baseline to week 52
- Proportion of patients reporting at least 1 episode of any hypoglycaemia (confirmed = symptomatic + blood glucose ≤50 mg/dL, major, other hypoglycaemia) during the 52-week double-blind treatment period
- Change in waist circumference from baseline to week 52
- Change in systolic BP from baseline to week 52
- Proportion of patients reporting at least one episode of hypoglycaemia (symptomatic + blood glucose ≤70 mg/dL [3.9 mmol/L]), see section 4.9.6) during the double-blind treatment period

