1.1.3 Other secondary objectives

To compare the effects of dapagliflozin plus metformin and dapagliflozin plus saxagliptin plus metformin with glimepiride plus metformin on the:

- Proportion of patients achieving HbA1c of <7% (and <7.5%) without confirmed hypoglycaemia at week 52
- Proportion of patients achieving HbA1c of <7% (and <7.5%) at week 52
- Proportion of patients achieving individually agreed HbA1c targets at week 52
- Proportion of patients achieving an HbA1c decrease of ≥1% with no weight gain at week 52
- Time spent below HbA1C target (<7%) (and <7.5%) during the 52-week double-blind treatment period
- Change in body mass index (BMI) from baseline to week 52

- Proportion of patients achieving weight reduction of $\geq 5\%$ from baseline to week 52
- Proportion of patients with weight gain $\geq 5\%$ from baseline to week 52
- Proportion of patients reporting at least 1 episode of hypoglycaemia (confirmed hypoglycaemia = symptomatic + blood glucose ≤50 mg/dL, major, other hypoglycaemia) during the 52 week double-blind treatment period
- Change in waist circumference from baseline to week 52
- Change in systolic BP from baseline to week 52

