4.3.1 Control of Type I error

The experiment-wise type I error will be controlled to a maximum of 5%. A hierarchical closed testing procedure will be employed such that key secondary endpoints will be considered for statistical significance (in terms of superiority) only if non-inferiority of the primary endpoint is concluded and that a key secondary endpoint will be considered for statistical significance only if the test ordered before it is found to be statistically significant. At each step, dapagliflozin plus saxagliptin added to metformin versus glimepiride added to metformin will be tested first followed by the test for dapagliflozin added to metformin versus glimepiride added to metformin except for the superiority tests of the primary endpoint and the endpoint of total body weight. The test of superiority for HbA1c will include only the comparison of dapagliflozin plus saxagliptin added to metformin versus glimepiride added to metformin. For total body weight, dapagliflozin added to metformin versus glimepiride will

be tested first followed by dapagliflozin plus saxagliptin added to metformin versus glimepiride added to metformin.

The following testing order will be followed for the overall type I error control:

- 1. Change from baseline in HbA1c at Week 52 (test for non-inferiority)
- 2. Proportion of patients reporting at least 1 episode of confirmed hypoglycaemia at Week 52 (test for superiority)
- 3. Change in total body weight from baseline to Week 52 (test for superiority)
- 4. Change from baseline in HbA1c at Week 52 (test for superiority of dapagliflozin plus saxagliptin added to metformin vs glimepiride added to metformin only)
- 5. Change in FPG from baseline to Week 52 (test for superiority)
- 6. Time to rescue at Week 52 (test for superiority)

The statistical comparisons will be done using a comparison-wise type I error of 5% (2-sided). For all other secondary variables and exploratory variables, nominal p-values will be reported without multiplicity controlled significance testing.

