4.9.6 Hypoglycaemia

Hypoglycaemic events occurring after the start of double blind study medication up to and including 4 days after the last double-blind dosing date will be considered as obtained during the double-blind treatment period and included in the summaries described below.

The proportion of patients with hypoglycaemic events and the number of hypoglycaemic events per patient will be summarised by treatment group. Hypoglycaemic events will also be categorised as follows:

• Major hypoglycaemic events: symptomatic events requiring external assistance due to severe impairment in consciousness or behaviour, with a capillary or plasma glucose

value <54 mg/dL (<3.0 mmol/L), and prompt recovery after glucose or glucagon administration

- Hypoglycaemia: Typical symptoms of hypoglycaemia accompanied by blood glucose \leq 70 mg/dL (3.9 mmol/L)
- Other episodes of hypoglycaemia: Symptoms of hypoglycaemia without a blood glucose reading or symptoms of hypoglycaemia accompanied by blood glucose >70 mg/dL (3.9 mmol/L)
- Confirmed hypoglycaemia: Typical symptoms of hypoglycaemia accompanied by blood glucose ≤50 mg/dL (2.8 mmol/L)
- Asymptomatic hypoglycaemia: An event not accompanied by typical hypoglycaemia symptoms but with measured plasma glucose \leq 70 mg/dL (\leq 3.9 mmol/L)

Hypoglycaemic events leading to discontinuation of study medication will be summarised by treatment. A summary of hypoglycaemic events over time by treatment will also be provided.

Summaries will be produced using data obtained prior to rescue medication only then repeated using all data regardless of use of rescue medication for patients in the Safety Analysis Set. A listing of patients will be produced for all hypoglycaemic events.

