- 34. Change from baseline in weight MMRM summary over time (Full analysis set)
- 35. Change from baseline in FPG MMRM summary over time (Full analysis set)
- 36. Time to rescue Kaplan Meier estimates (Full analysis set)
- 37. Proportion meeting HbA1c criteria without confirmed hypoglycaemia at week 52 (Full analysis set)
- 38. Proportion meeting HbA1c criteria at week 52 (Full analysis set)
- 39. Proportion achieving individually agreed HbA1c targets at week 52 (Full analysis set)
- 40. Proportion with a HbA1c decrease >=1% with no weight gain (Full analysis set)
- 41. Time spent below HbA1c target (<7% and <7.5%) (Full analysis set)
- 42. Change in BMI from baseline to week 52 (LOCF) (Full analysis set)
- 43. Proportion with a weight reduction >=5% or a weight gain >=5% (Full analysis set)
- 44. Proportion with at least 1 episode of any hypoglycaemia (Full analysis set)
- 45. Change in waist circumference from baseline to week 52 (LOCF) (Full analysis set)
- 46. Change in systolic blood pressure from baseline to week 52 (MMRM) (Full analysis set)
- 47. Proportion with at least one episode of hypoglycaemia (symptomatic + blood glucose ≤70 mg/dL [3.9 mmol/L]) (Full analysis set)
- 48. Change from baseline over time in efficacy variables (observed values) (Full analysis set)

Exploratory

- 49. SF-36v2 scores and change from baseline (Full analysis set)
- 50. HFS-II worry scale mean score and change from baseline (Full analysis set)
- 51. IWQOL-Lite scores and change from baseline (Full analysis set)
- 52. Waist-to-hip ratio (Full analysis set)

Adverse Events

- 53. Overall adverse events summary (Safety analysis set) with data prior to rescue treatment only
- 54. Overall adverse events summary (Safety analysis set) including all data regardless of rescue
- 55. Adverse events by SOC and PT (Safety analysis set) with data prior to rescue treatment only
- 56. Adverse events by SOC and PT (Safety analysis set) including all data regardless of rescue
- 57. Adverse events by SOC and PT by age categories (Safety analysis set) including all data regardless of rescue
- 58. Adverse events by SOC and PT by gender (Safety analysis set) including all data regardless of rescue
- 59. Adverse events by SOC and PT by female age categories (Safety analysis set) including all data regardless of rescue
- 60. Adverse events by SOC and PT by race (Safety analysis set) including all data regardless of rescue

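### The 'any hypoglycaemia' endpoint, as listed, leaves out unassisted symptomatic episodes at 51-70 mg/dL and so does not contain the ≤70 mg/dL endpoint beside it

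*SAP*

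**What the plan says.** Section 3.3 lists, among the other secondary efficacy variables, "Proportion of patients reporting at least 1 episode of any hypoglycaemia (confirmed = symptomatic + blood glucose ≤50 mg/dL, major, other hypoglycaemia"). The matching objective in section 1.1.3 gives the same three components: "confirmed hypoglycaemia = symptomatic + blood glucose ≤50 mg/dL, major, other hypoglycaemia) during the 52 week double-blind treatment period".

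Section 4.9.6 is where the SAP defines the event categories:

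- **Confirmed:** typical symptoms with glucose ≤50 mg/dL.
- **Major:** symptomatic, needing external assistance because of severe impairment, with a glucose "value <54 mg/dL (<3.0 mmol/L), and prompt recovery after glucose or glucagon administration".
- **Other episodes:** "Symptoms of hypoglycaemia without a blood glucose reading or symptoms of hypoglycaemia accompanied by blood glucose >70 mg/dL".
- **Hypoglycaemia:** typical symptoms with glucose ≤70 mg/dL. This category is not among the three components.
- **Asymptomatic:** glucose ≤70 mg/dL without typical symptoms. This is not among them either.

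Section 3.3 also carries a separate variable, "Proportion of patients reporting at least one episode of hypoglycaemia (symptomatic + blood glucose ≤70 mg/dL [3.9 mmol/L]), see section 4.9.6". Both variables are analysed by logistic regression (Table 11, section 4.8.2). Planned Table 44 in section 7.1.1 reports "Proportion with at least 1 episode of any hypoglycaemia (Full analysis set"), and planned Table 47 reports the ≤70 mg/dL variable. Neither the analysis sections nor the missing-data rules in 4.6.2 widen the definition of 'any'.

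**The concern.** A variable called 'any hypoglycaemia' should contain every narrower hypoglycaemia variable. Read against 4.9.6, this one has a hole in the middle of the glucose scale. It takes symptomatic episodes at or below 50 mg/dL, and symptomatic episodes above 70 mg/dL or without a reading, but drops most of those in between.

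Two things are at stake. First, Table 44 could show a smaller proportion than Table 47, which is incoherent for a reader who takes the label at face value. Second, two programmers could derive the variable differently: one using the 4.9.6 category for 'other', the other treating 'other' as whatever is left over.

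**Working it through.** The SAP has no figure of its own to reproduce here; the check is one of classification.

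**Step 1. Classify single symptomatic episodes by the 4.9.6 definitions.** The listed endpoint is confirmed or major or other.

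| Glucose (mg/dL) | Unassisted: category | In 'any' list? | Assisted: category | In 'any' list? | In ≤70 endpoint? |
|---|---|---|---|---|---|
| ≤50 | confirmed | yes | confirmed, major | yes | yes |
| 51-53 | symptomatic ≤70 only | **no** | major | yes | yes |
| 54-70 | symptomatic ≤70 only | **no** | symptomatic ≤70 only | **no** | yes |
| >70 | other | yes | other | yes | no |
| no reading | other | yes | other | yes | no |

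The table uses whole-number readings; on exact values the unassisted gap runs from just above 50 up to 70 mg/dL. The assisted 51-53 row assumes that the remaining major criteria (severe impairment, prompt recovery) are met; an episode that fails them also falls into the gap. Asymptomatic episodes at ≤70 mg/dL are outside the list throughout.

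**Step 2. Compare Table 44 with Table 47.** Confirmed and major episodes are both symptomatic with glucose ≤70 mg/dL, so a patient with either is in both tables. Within an arm, let

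- a = patients whose symptomatic episodes all lie in the omitted band (in Table 47, not in Table 44);
- b = patients whose symptomatic episodes are all in the other category (in Table 44, not in Table 47).

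Then count(Table 44) − count(Table 47) = b − a, and Table 44 is lower whenever a > b. With the 290 evaluable patients per arm from section 1.3, each net patient is 1/290 = 0.34 percentage points.

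**Step 3. Scale, on assumed rates only.** The SAP gives no event rates. Suppose the true proportions with any symptomatic episode were 20% and 5% in two arms, and that 30% to 80% of those patients, equally in both arms, had only omitted-band episodes.

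| Share omitted | Reported rates | Odds ratio | Risk ratio |
|---|---|---|---|
| none | 20% v 5% | (0.20/0.80)/(0.05/0.95) = 4.75 | 4.0 |
| 30% | 14% v 3.5% | (0.14/0.86)/(0.035/0.965) = 4.49 | 4.0 |
| 80% | 4% v 1% | (0.04/0.96)/(0.01/0.99) = 4.13 | 4.0 |

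The reported levels can change a great deal while the contrast changes little. The constant risk ratio follows from assuming the same omitted share in both arms. The method can change too: section 4.5.7 replaces logistic regression by Fisher's exact test when any arm has fewer than 5 responders. In the 80% row the low-rate arm has 290 × 0.01 = 2.9 expected responders, against 290 × 0.05 = 14.5 without omission. This shows the mechanism; it is not a forecast.

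**Step 4. Test the repair.** Adding the symptomatic ≤70 mg/dL category covers every row of the first table, so the endpoint then contains both the confirmed and the ≤70 mg/dL endpoints.

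**The case against.** The strongest reply is that 'any' shows the intent and that the closing 'other hypoglycaemia' means everything else. The label in 4.9.6 is slightly different (other episodes), and this variable, unlike the confirmed and ≤70 mg/dL variables, does not refer to 4.9.6. On that reading no symptomatic patient is missed. The reading is possible, but the SAP states it nowhere, and it competes with a defined category of nearly the same name. It would also leave open whether asymptomatic events at ≤70 mg/dL enter as part of the remainder.

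The second reply is that little is lost, and most of that stands. Table 47 gives the ≤70 mg/dL comparison, the safety summaries show hypoglycaemic events by category and arm, and section 4.3.1 says "For all other secondary variables and exploratory variables, nominal p-values will be reported without multiplicity controlled significance testing". Table 47 does not fully substitute, however: it excludes symptomatic events without a reading or above 70 mg/dL, and its counts cannot be added to those of Table 44 because patients overlap. As written, neither table gives the between-arm comparison of all symptomatic hypoglycaemia that the label promises.

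It is also fair that nothing in the SAP shows that a will exceed b. The reversal of the two tables is a possibility, not a prediction.

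**Conclusion.** The concern holds. Taken with the 4.9.6 definitions, the component list in 1.1.3 and 3.3 omits unassisted symptomatic episodes at 51-70 mg/dL and assisted ones at 54-70 mg/dL, so the 'any' endpoint is not a superset of the ≤70 mg/dL endpoint. This rests on reading 'other' as the 4.9.6 category, the only definition the SAP supplies.

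The undercount cannot be derived from the document. No dilution of the treatment contrast and no effect on type I error are claimed. The variable lies outside the testing hierarchy, and the primary and key secondary results are unaffected. It should be corrected because the rule is wrong as written and the correction is nearly free.

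**What to change.** In sections 1.1.3 and 3.3, and in the title or footnote of planned Table 44, define 'any hypoglycaemia' by naming the 4.9.6 categories: symptomatic with glucose ≤70 mg/dL (which already contains confirmed ≤50 mg/dL), major, and other episodes, with a reference to 4.9.6. State explicitly whether asymptomatic events at ≤70 mg/dL count; the present list does not include them.

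The cost is SAP wording and one derivation line, to be settled before unblinding. All the categories are already defined and collected.

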3.4 Safety variables

The following safety variables (defined in Section 4.9) will be analysed:

- Incidence of adverse events (AEs) (including serious adverse events (SAEs), Hypoglycaemic AEs and AEs of special interest (AEOSI))
- Proportion of patients withdrawing from study treatment due to hypoglycaemia
- Change from baseline in clinical laboratory parameters
- Change from baseline in vital signs (pulse and blood pressure)

3.5 Pharmacokinetics

NA

3.6 Patient reported outcomes (PROs)

All patients will complete the SF-36v2 Health Survey, HFS-II Worry Scale and the IWQOL-Lite survey. The SF-36 addresses 8 health concepts: physical functioning; role - physical; bodily pain; general health; vitality; social functioning; role - emotional; and mental health. SF-36 also includes a single item that provides an indication of perceived change in health. Its score ranges from 0 to 100 with higher scores indicating better health.

The HF-II measures the fear of hypoglycaemia in adults with T2DM. Items in the HFS-II Worry scale describe the concerns that patients may have about their hypoglycaemic episodes (e.g., being alone, episodes occurring during sleep, or having an accident). Each is measured on a 5 point scale (Never to Always).

The IWQOL-Lite is a 31-item self-reported assessment of quality of life in overweight or obese individuals. It scores on 5 dimensions: physical function (11 items); self-esteem (7 items); sexual life (4 items); public distress (5 items); and work (4 items). A global score (sum of scale scores) is also included. Participants are asked to rate items with respect to the past week on this instrument (from never true to always true). Scores on the IWQOL-Lite (domains and global score) range from 0 to 100 with higher scores indicating poorer quality of life.

The following exploratory endpoints related to patient reported outcomes will be summarised:

- Change in the short form 36-item health survey (SF-36) scores from baseline to week 52
- Change in the Hypoglycaemia Fear Survey (HFS-II) Worry scores from baseline to week 52
- Change in the Impact of Weight on Quality of Life (IWQOL)-Lite survey scores from baseline to week 52

3.7 Additional exploratory endpoints

• Change in waist:hip ratio from baseline to week 52

3.8 Health economics

NA

4. ANALYSIS METHODS

4.1 General principles

Continuous variables will be presented with mean; median; 25th and 75th percentiles; standard deviation (SD); minimum; maximum; and (if appropriate) the number of non-missing observations. Categorical data will be displayed via absolute and relative frequencies for each category, including a category labelled as 'missing' when appropriate. The 'missing' category will not contribute to the denominators of relative frequencies.

Demographic and baseline characteristics will be summarised using frequency distributions and descriptive statistics using the Randomised patients set, for each treatment group as well as for all patients combined. Key baseline characteristics that will be summarised include: age; gender; race; ethnicity; country; body weight; BMI; duration of T2DM; baseline FPG; baseline HbA1c and baseline eGFR. Baseline is defined as the last measurement prior to the first dose of double blind study medication or as the last non-missing value of the visit 1 or visit 2 assessment for those subjects without a first dose start date. No statistical tests will be performed to compare treatment groups at baseline.

4.2 Primary analysis

The primary analysis will be carried out for the primary objective using data from the Full Analysis set. It will use values prior to rescue treatment or discontinuation (more than 8 consecutive days off treatment, see section 4.6.2).

4.2.1 Objectives and hypotheses

The combination of metformin and a sulphonylurea (glimepiride) is a standard therapy in the treatment of type 2 diabetes and has been shown to reduce HbA1c.

The primary objective of this study is to demonstrate the non-inferiority of dapagliflozin and dapagliflozin plus saxagliptin as add-on therapies to metformin compared to glimepiride as add-on therapy to metformin for the primary efficacy variable (change in HbA1c from baseline to week 52).

The null hypothesis H_0 (given below) will be tested against the alternative hypothesis H_A ($\alpha = 0.025$, one-sided):

$$H_0$$
: $\mu_t - \mu_c \ge 0.30\%$,

$$H_A$$
: $\mu_t - \mu_c < 0.30\%$

where μ_t denotes the mean absolute change in HbA1c from baseline to week 52 in patients treated with dapagliflozin added to metformin and dapagliflozin plus saxagliptin added to metformin (test medication); μ_c denotes the mean absolute change in HbA1c from baseline to week 52 in patients treated with glimepiride added to metformin (active control). The non-inferiority margin is determined to be 0.30% (in absolute terms). A difference of 0.30% or

less, in HbA1c change from baseline to week 52 between the treatment groups, is considered clinically equivalent (from a medical point of view). Non-inferiority will be assessed using the 2-sided 95% Confidence Interval (CI) of the adjusted mean difference between dapagliflozin or dapagliflozin plus saxagliptin and glimepiride. If the upper limit of the 2-sided 95% CI is less than 0.30% then dapagliflozin or dapagliflozin plus saxagliptin will be considered to be non-inferior to glimepiride.

To preserve the Type I error \leq 0.025 (one-sided), a hierarchical testing procedure will be used as follows:

- First test dapagliflozin plus saxagliptin versus glimepiride
- If non-inferiority is achieved then test dapagliflozin versus glimepiride

4.3 Secondary analysis

Four key secondary endpoints have been identified:

- 1. Proportion of patients reporting at least 1 episode of confirmed hypoglycaemia (symptomatic + blood glucose ≤50 mg/dL) during the double-blind treatment period
- 2. Change in total body weight from baseline to week 52
- 3. Change in FPG from baseline to week 52
- 4. Time to rescue during the 52 week treatment period

The hypotheses of the above four key secondary endpoints will test for superiority of dapagliflozin and dapagliflozin plus saxagliptin over glimepiride when used as add-on therapy to metformin - where superiority implies smaller proportions of patients experiencing at least one episode of hypoglycaemia, greater reductions in body weight and FPG; and a longer time to rescue treatment.

A superiority test of the dapagliflozin plus saxagliptin added to metformin group versus the glimepiride added to metformin group will also be conducted for the primary efficacy variable of change in HbA1c from baseline to week 52.

4.3.1 Control of Type I error

The experiment-wise type I error will be controlled to a maximum of 5%. A hierarchical closed testing procedure will be employed such that key secondary endpoints will be considered for statistical significance (in terms of superiority) only if non-inferiority of the primary endpoint is concluded and that a key secondary endpoint will be considered for statistical significance only if the test ordered before it is found to be statistically significant. At each step, dapagliflozin plus saxagliptin added to metformin versus glimepiride added to metformin will be tested first followed by the test for dapagliflozin added to metformin versus glimepiride added to metformin except for the superiority tests of the primary endpoint and the endpoint of total body weight. The test of superiority for HbA1c will include only the comparison of dapagliflozin plus saxagliptin added to metformin versus glimepiride added to metformin. For total body weight, dapagliflozin added to metformin versus glimepiride will

be tested first followed by dapagliflozin plus saxagliptin added to metformin versus glimepiride added to metformin.

The following testing order will be followed for the overall type I error control:

- 1. Change from baseline in HbA1c at Week 52 (test for non-inferiority)
- 2. Proportion of patients reporting at least 1 episode of confirmed hypoglycaemia at Week 52 (test for superiority)
- 3. Change in total body weight from baseline to Week 52 (test for superiority)
- 4. Change from baseline in HbA1c at Week 52 (test for superiority of dapagliflozin plus saxagliptin added to metformin vs glimepiride added to metformin only)
- 5. Change in FPG from baseline to Week 52 (test for superiority)
- 6. Time to rescue at Week 52 (test for superiority)

The statistical comparisons will be done using a comparison-wise type I error of 5% (2-sided). For all other secondary variables and exploratory variables, nominal p-values will be reported without multiplicity controlled significance testing.

